3 OBJECTIVES AND OUTCOME MEASURES/ENDPOINTS

The research question of the study has already been defined by the call HTA 19/76 "For young people with anorexia nervosa, is it feasible to conduct a trial to examine the benefits and harms of prescribing atypical antipsychotics to those who have not responded to first-line treatments?" We have chosen olanzapine as the most promising medication to test in this patient group, and we have defined study aims accordingly.

3.1 Primary objective

The primary objective of this feasibility study is to assess the **feasibility** of carrying out such a trial to inform a future definitive RCT. This includes

- To assess the proportion of patients in different settings (adolescent/adult, inpatient/daycare/ outpatient) who
 - agree to take olanzapine (un-blinded, real-life conditions)
 - adhere to olanzapine
 - complete all study assessments and questionnaires at the five assessment points.

3.2 Secondary objectives

Secondary objectives are to test the feasibility of data collection procedures (completeness and summary statistics) for the following measures:

Page 21 of 60

- Measures at baseline (demographics, smoking, alcohol, and substance abuse)
- Body weight and BMI
- Eating disorder psychopathology
- General psychopathology
- Health economic and quality of life assessment completed by both participants and their carers
- Drug adherence (to examine different methods to measure adherence (questionnaire, pill count, olanzapine plasma level)
- Drug safety (to examine the quality of reporting of adverse events)

Also to use qualitative methods to assess willingness to participate in a blinded, placebo-controlled RCT

3.2.1 Exploratory Objectives

- Treatment as usual (TAU)(to examine and document what TAU means in practice)
- Assess patients experience of recruitment and treatment (to use qualitative methods to study patients' experience of recruitment and treatment, acceptability and reasons for adherence and non-adherence)
- Explore change in the measures as listed in section 3.2 to inform a future definitive RCT.

For further information on the primary, secondary, and exploratory objectives see next section on outcome measures.

3.3 Outcome measures/endpoints

3.3.1. Feasibility of questionnaires and assessments

We will assess the applicability of potential future RCT outcomes, assessment measures and completion of assessments. Questionnaires not completed in >25% will not be included in a potential application for a randomized pilot study or full RCT following this feasibility. This feasibility study includes full assessments at baseline, after 8 weeks, after 16 weeks, after 6 months and after 12 months. The assessments will be conducted by the researcher with the support of the patients' clinical service teams. Qualitative interviews will take place at baseline and after 16 weeks. Furthermore, patients who refuse to enter the study will also be offered the opportunity to participate in a qualitative interview aimed at understanding their reasons for refusing to participate in the OPEN study. They will be conducted by the qualitative researcher; see flow chart.

During study-related activities, the intake of olanzapine and the study assessments, 12- to 15-year-old children will be accompanied by a trusted adult, which may be a parent, carer or a clinical staff member entrusted with the clinical care of the patient.

3.3.2. Body weight and BMI

Patients' weight and height will be measured objectively and BMI calculated during the assessments at baseline, 8 weeks, 16 weeks, 6 months, 12 months.

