3.4 Primary endpoint/outcome

Primary objective: feasibility

Primary endpoints: Assessing the proportion of patients in different settings, examining different methods to measure adherence (questionnaire, pill count, olanzapine plasma level). Important measurement time points are the baseline and 12 months after baseline.

Summary statistics will be presented on the following for feasibility and may include estimation of confidence intervals:

Patients approached, screened and included in the study

Adherence, completed physical assessments (including BMI measurement) and questionnaires

Willingness to take part in an RCT

Elements that constitute TAU

Summary statistics on psychopathology, general psychopathology and quality of life assessments and change in BMI will also be reported.

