6.1 Inclusion criteria

- Adolescent or young adults (12-24 years old).
- Receiving inpatient, day care or outpatient treatment
- Diagnosed with AN, or atypical AN, according to DSM-5.

- Patients have gained <2 kg within at least one month of TAU. Outpatients should have attended ≥4 therapeutic sessions. 2 kg within the time frame of at least one month appears most appropriate to predict further therapy response or non-response to the current treatment according to our systematic review and meta-analysis on early response and treatment outcome prediction [84].
- The patient can read and write in English.
- Written Informed consent to participate

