10.3.4 Exploratory analyses

- We will also perform exploratory analyses looking at change over time in measures listed in Section 10.3.3 to inform a future definitive study design. Such analyses will use appropriate longitudinal modelling approaches; further details will be covered in the Statistical Analysis plan.
- Elements that constitute TAU will be described.
- Patient experience of recruitment and treatment, acceptability and reasons for adherence and nonadherence will be ascertained in qualitative interviews which will be performed, transcribed and analysed.

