10.3.5 Qualitative analysis

We will conduct individual qualitative interviews in a subgroup (estimated 30 individuals) of young people with AN who either agree or decline to participate in the OPEN feasibility study. There are two main aims of the qualitative interviews: deciphering the barriers of inclusion for the study and also follow up interviews with questions concerning reflections of their participation. Interviews will examine the decision-making process and the perceived risks and advantages of taking olanzapine within the study. At the point of recruitment, participants will be asked why they agreed or refused to take part in the study. We will also ask for their permission to share their details for subsequent publications. Those who are

Page 47 of 60

recruited to OPEN will be interviewed after the 16-week assessment point about their perceptions prior to participation and their subsequent experiences of olanzapine treatment and the study design, including the perceived burden of completing outcome measures and attitudes towards randomisation in a future clinical trial. We will interview people who have adhered to olanzapine as well as people who have dropped out. The qualitative researcher will aim for 'empathic neutrality', posing open and non-leading questions that invite participants to recount their experiences of the study and treatment from their perspective.

Purposive sampling will be conducted based on gender, age, recruitment source, BMI at baseline and adherence to explore a range of perspectives. A further 10-15 interviews with health care professionals across settings will explore the perceived challenges and facilitators to recruitment and retention. Qualitative data will be analysed using the Framework Approach [85] to facilitate analysis within and between individual cases and groups of participants. The thematic framework will draw on a priori issues around the acceptability of the intervention and design study, but also be responsive to emergent themes.

All qualitative interviews will be carried out by the UK qualitative researcher (TBA2).

Two PhD student studying at King's College London under the supervision of [name] and [name], will assist [name] will the qualitative data collection and analysis.

10.4 Subgroup analysesWe do not plan any subgroup analyses.

10.5 Adjusted analysis We do not plan any adjusted analyses.

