11 DATA MANAGEMENT

11.1 Data collection tools and source document identification

A web-based electronic data capture (EDC) system will be designed, using the InferMed Macro 4 system. The EDC will be created in collaboration with the trial analyst/s and the CI and maintained by the King's Clinical Trials Unit (KCTU) for the duration of the project. It will be hosted on a dedicated server within KCL.

Participant age will be entered on the EDC, initials, date of birth, NHS number, email addresses, participant names and addresses, and full postcodes will not be entered into the EDC. No data will be entered into the EDC system unless a participant has signed a consent form to participate in the trial. Source data will be entered centrally by the coordinating study team typically within 5 days of data collection by authorized staff onto the EDC by going to www.ctu.co.uk and clicking the link to access the MACRO 4 EDC system. A full audit trail of data entry and any subsequent changes to entered data

Page 49 of 60

will be automatically dated and time stamped, alongside information about the user making the entry/changes within the system.

Patient self-reported measures will be collected via Qualtrics, a cloud-based subscription software platform for experience management and entered into the EDC by authorized research staff.

The CI will undertake appropriate reviews of the entered data for the purpose of data cleaning and will request amendments as required. No data will be amended independently of the study site responsible for entering the data.

At the end of the trial, the site PI will review all the data for each participant and provide electronic signoff that all the data are complete and correct. At this point, all data can be formally locked for analysis.

The InferMed Macro 4 system also includes an e-Case Report Form (eCRF) database in order to enter individual patient data throughout the protocol. The system can be programmed to perform validation checks, such as range checks to prevent data entry errors. Missing data codes are routinely programmed into all fields, for ease of analysis. A standard feature of InferMed MACRO data entry system is the built-in audit trail on all data fields, the automatic saving of data as you leave a form, and the ability to maintain a record of 'source data verification' checks.

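### Weight and BMI change is specified only in raw units for patients aged 12 to 24, so expected adolescent growth is mixed into a summary meant to inform the RCT (minor)

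*Protocol*

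**What the plan says.** - **Population.** Section 6.1 admits "Adolescent or young adults (12-24 years old", so growing adolescents and adults form one cohort. Section 4 states that the design has one arm and no comparator.
- **Measure.** Section 3.3.2 has weight and height measured and "BMI calculated during the assessments at baseline", with the same repeated at each of the four later visits up to 12 months. Section 3.5 lists height, weight and BMI, and section 10.3.3 lists body weight and BMI among the descriptive summaries. No z-score, centile or percent median BMI appears anywhere.
- **Use.** Section 3.4 names baseline and 12 months as the important time points and adds that "change in BMI will also be reported". Sections 3.6.3 and 10.3.4 explore change over time to inform a definitive study. On method, section 10.3.4 says: "Such analyses will use appropriate longitudinal modelling approaches; further details will be covered in the Statistical Analysis plan".
- **Adjustment.** Section 10.4 plans no subgroup analyses. Section 10.5 reads: "We do not plan any adjusted analyses".
- **Age data.** Section 11.1 admits age to the EDC but keeps date of birth and other identifiers out of it: "Participant age will be entered on the EDC, initials, date of birth, NHS number, email addresses" opens the sentence that says so. Section 7.1.2 lists age and gender among the screening items for the eCRF.
- **Comparability.** Section 3.3.3 accepts that adult and adolescent scores are not always comparable and gives a rule for that case, but only for questionnaires.

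**The concern.** Below 18, the meaning of a kilogram or a BMI unit changes with age and height. Three effects are at work over 12 months:

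- weight rises with height even when BMI stays constant;
- the BMI expected of a healthy peer rises with age, so some rise in raw BMI is needed just to keep the same relative position;
- height growth without weight gain lowers raw BMI although no weight was lost.

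Raw change therefore combines recovery with growth, and not always in the same direction. With no comparator, nothing in the design removes the growth part. Section 10.1 says the study should supply key parameters for a future trial, including a justified primary outcome and its timing. If weight or BMI is considered for that role, the change seen here would be harder to read than it needs to be, most of all in the youngest patients at 12 months.

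**Working it through.** **The plan's own precision figure.** Section 10.1 gives margins of 12.2% at 70% adherence and 13.3% at 50%, with n = 55. The formula 1.96 x sqrt(p(1-p)/(n-1)) reproduces both: 1.96 x sqrt(0.21/54) = 12.2% and 1.96 x sqrt(0.25/54) = 13.3%. Neither depends on BMI, so the sample size is unaffected.

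**Growth part of a pooled BMI change.** Let f be the share of participants under 18 and s the yearly rise in the reference median BMI at their ages. Adults are taken to have no expected rise, and the rise is taken as linear. The expected-growth part of the pooled 12-month mean change is f x s. The protocol gives neither input, so both ranges are assumptions.

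| f | s = 0.2 | s = 0.5 | s = 0.8 |
|---|---|---|---|
| 0.25 | 0.05 | 0.125 | 0.20 |
| 0.50 | 0.10 | 0.25 | 0.40 |
| 0.75 | 0.15 | 0.375 | 0.60 |

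(kg/m2 at 12 months)

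At 8 weeks, multiplying by 8/52 gives 0.01 to 0.09 kg/m2, which is negligible. For scale, section 2.1 reports a BMI rise of 1.8 kg/m2 in an audit of 12 inpatients. The 12-month range is 3% to 33% of that (0.05/1.8 to 0.60/1.8), but the audit covered 8 weeks, so this is a yardstick and not a like-for-like ratio.

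**Direction.** Assume a BMI of 15 and a height of 1.55 m, with height growth g over the year.

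- Weight needed to hold BMI: 15 x [(1.55+g)^2 - 1.55^2]. This gives 0.5 kg for g = 1 cm and 2.8 kg for g = 6 cm. Weight rises and BMI does not change.
- BMI change if no weight is gained: 15 x 1.55^2/(1.55+g)^2 - 15. This gives -0.2 for 1 cm and -1.1 for 6 cm. Weight does not change and BMI falls.

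The same growth thus appears as a gain in one summary or a loss in the other.

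**Can BMI be standardised from what is captured?** Age, gender, height and weight are all recorded, so yes, approximately (taking recorded gender to give the sex that the reference needs). If age is held only in whole years and set to mid-year, it is wrong by at most 0.5 years. The reference median is then off by at most 0.5 x s, or 0.10 to 0.40 kg/m2. If baseline age is carried forward by the scheduled visit times, that offset largely cancels in within-patient change. The documents do not say whether age is in whole years.

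**The case against.** The strongest reply is that little depends on this. The main outcome is feasibility (section 10.3.2), section 2.4 says the study is not meant to establish efficacy, and change over time is only explored or described. Derived variables and the form of change summaries are commonly left to a SAP, and section 10.3.4 defers modelling detail to one. A single pooled mean is inferred from sections 10.4 and 10.5 and is not stated. Section 3.1 itself breaks the primary proportions down by adolescent and adult setting. All of this stands and limits the severity. It does not remove the point, because the raw measure and the exclusion of subgroup and adjusted analyses are fixed in the protocol. A SAP that split or adjusted by age would depart from sections 10.4 and 10.5.

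Three stronger readings are tempting, and the documents do not support them.

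- *Growth is counted as response.* No weight or BMI response endpoint exists. The only weight threshold, a gain below 2 kg in at least one month, is an entry criterion (section 6.1).
- *Keeping date of birth out of the EDC prevents standardisation.* Age is entered, and section 11.2 keeps identifying factors in a separate database linked by study number. Only the precision of age is open.
- *Growth can equal the drug effect.* At an assumed height of 1.50 m and BMI of 16, 6 cm of growth adds 16 x (1.56^2 - 1.50^2) = 2.9 kg in a year, against 6.7 - 4.2 = 2.5 kg in the largest cited RCT (section 1.2). That RCT figure is a 16-week difference between arms in patients aged 16 to 65. Pro-rated to 16 weeks, the growth is about 0.9 kg, and expected growth would be common to randomised arms. Section 1.1 also lists growth retardation as a consequence of the illness, so growth of that size cannot be presumed.

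**Conclusion.** The point holds as a minor one. For participants under 18, the plan as written mixes expected growth with recovery in its descriptive 12-month change in weight and BMI, although section 3.3.3 already recognises the comparability problem for questionnaires. Under the assumed ranges, the growth part of a pooled BMI change is about 0.05 to 0.60 kg/m2 at 12 months (0.25 at the middle values) and under 0.1 at 8 weeks. These figures rest on an assumed adolescent share, an assumed linear reference slope and pooling over age. For an individual, the effect on weight and BMI can go either way. The sample size and the primary feasibility results are unaffected.

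**What to change.** - In sections 3.3.2, 3.4 and 10.3.3, add an age- and sex-standardised BMI (BMI-for-age z-score or percent median BMI) for participants under 18, reported beside raw BMI.
- Summarise change in weight and BMI separately for adolescents and adults, and amend section 10.4 to allow this. The split matches the adolescent and adult settings already used in section 3.1.
- In section 11.1, specify that age is entered in years and months. Date of birth can stay out of the EDC.

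The cost is one derived variable, one more precise age field and smaller groups in the descriptive summaries. No assessment is added, since height and weight are already taken at every visit.

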3.3.3. ED psychopathology

ED psychopathology, general psychopathology, health economic outcomes and quality of life will be measured using questionnaires. Scores for adults and adolescents are comparable for some questionnaires, e.g., the Epworth Sleepiness Scale (ESS) and the Epworth Sleepiness Scale - Child Adolescent (ESS-CHAD) but not all. If not comparable, scores will be converted into binary outcomes, e.g., scores of the Depression Anxiety Stress Scales (DASS) and Revised Children's Anxiety and Depression Scale (RCADS).

Eating Disorder Examination-Questionnaire (EDE-Q): The EDE-Q is a questionnaire assessing key behavioural features and associated psychopathology of eating disorders [49]. It includes four subscales: Restraint, weight concern, shape concern, eating concern

Revised Beliefs about Voices Questionnaire (BAVQ-R; A/a>15 years): The BAVQ-R is a self-report measure of patients' beliefs, emotions and behaviour about auditory hallucinations [50]. We have chosen this questionnaire as people with AN often report experiencing an internal voice. This so-called "anorexic voice" comments on the individual's eating, weight and shape and instructs the individual to restrict or compensate [51]. This questionnaire will provide information about patients' emotional and behavioural reactions to these auditory hallucinations. This will allow conclusions not only about the content and form, but also about the meaning given to these auditory hallucinations [50].

The Self-regulation of Eating Behaviour Questionnaire (SREBQ): The SREBQ is a self-reported measure of the patients' capacity for management of behaviour, thoughts, feelings, attention and environment in the pursuit of personal goals and measuring change in response to self-regulation interventions in adults [52]. The questionnaire will give additional information on food cravings, dietary restraint and the capacity for self-regulation in patients with AN [53].

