3.3.4. General psychopathology

As AN has been found to be associated with depressive disorder [4], anxiety disorders [5], OCD [6] and autism spectrum disorder [7], shows an overlap with schizophrenia on a symptomatic and genetic level [53,64], and because we are testing olanzapine, an antipsychotic drug [55], we decided to include scales measuring general psychopathology related to the mentioned disorders.

Depression Anxiety Stress Scales (DASS): The DASS [56] is a 42-item instrument designed to measure the three related negative emotional states of depression, anxiety and stress. Over 20 years, it has been vastly used in research and has been evaluated in large clinical samples to investigate symptoms of depression, anxiety and stress (e.g. [56,57]).

For adolescents, we will use the Revised Children's Anxiety and Depression Scale (RCADS): The RCADS is a 47-item questionnaire that measures the frequency of various symptoms of anxiety and low mood. This questionnaire is commonly used in studies involving adolescents. Therefore, we use it in addition to the DASS. The RCADS produces a total anxiety and low mood score, and separate scores for each of the follow sub-scales [58]: Separation anxiety, social phobia, generalised anxiety, panic, obsessive compulsive, total anxiety and low mood.

Yale-Brown Obsessive-Compulsive Scale (Y-BOCS): The Y-BOCS [59] is a clinician-administered 10item scale designed to measure the severity and type of symptoms in people with OCD. The symptoms assessed are obsessions and compulsions. The Y-BOCS is sensitive to changes in OCD symptoms. Therefore, it has been extensively used in clinical studies in over 30 years (e.g. [60,61]). The Y-BOCS version for adolescents is the Children's Yale-Brown Obsessive-Compulsive Scale (CY-BOCS).

Columbia Suicide Severity Rating Scale (C-SSRS): The C-SSRS is a suicidal ideation rating scale created to evaluate suicidality in adolescents and adults (12 years and up) [62]. It rates an individual's degree of suicidal ideation and has been used successfully in research in adolescent as well as adult populations (e.g. [63,64]).

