4 TRIAL DESIGN

The design of this feasibility study is open treatment of 55 patients with olanzapine for 12 months. Participants will be examined at baseline, and at 8 weeks, 16 weeks, 6 months and 12 months after start of treatment. This is a one-arm open treatment design, there is no placebo and no comparator.

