10 STATISTICS AND DATA ANALYSIS

10.1 Sample size calculation

According to the guidance given by the NIHR Research Design Service London, https://www.rds-london.nihr.ac.uk/resources/justify-sample-size-for-a-feasibility-study/, a reasonable sample size can be

Page 44 of 60

between 30 and more than 50 [94,95]. According to the call, our proposed feasibility study should cover: Willingness to accept and adhere to the intervention; a demonstration that adherence can be measured; estimated numbers of young people potentially eligible for recruitment; key parameters of a potential future trial to include a justification of the choice and timing of an appropriate primary outcome measure. Given the variety of parameters, a figure at the upper end of the recommended range seemed plausible to us. We also have also carried out a sample size calculation for this feasibility study based on estimating the feasibility parameter "rate of adherence": Assuming that 70% of patients took olanzapine for at least 16 weeks, a sample size of 55 patients can estimate a 95% confidence interval for this parameter with 12.2% margin of error (i.e., expected CI from 57.8% to 82.2%; for a more extreme attrition rate of 50% the margin of error increases to 13.3%).

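### Section 3.3.3 makes dichotomising the remedy for non-comparable adult and adolescent scales, without committing to report their continuous scores

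*Protocol*

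**What the plan says.** Section 3.3.3 first notes that "Scores for adults and adolescents are comparable for some questionnaires" and gives the ESS and ESS-CHAD as an example. For the rest it states, without qualification, "If not comparable, scores will be converted into binary outcomes", with DASS and RCADS as the example. No cut-off is named there.

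Sections 3.2.1 and 3.6.3 say that change in the measures will be explored to inform a future definitive trial. Section 10.3.4 plans "exploratory analyses looking at change over time in measures listed in Section 10.3.3 to inform a future definitive study design" and leaves the longitudinal modelling details to the SAP. Section 10.1 lists key parameters of a future trial, including the choice and timing of its primary outcome, among the things the study should cover.

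Sections 3.2, 3.4, 3.5 and 10.3.3 promise completeness, summary statistics or descriptives for the psychopathology measures. None says whether these are on the raw or the binary scale. Section 10.4 plans no subgroup analyses.

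On who completes what, section 3.3.4 says of the RCADS in adolescents: "Therefore, we use it in addition to the DASS". The trial summary presents the RCADS as the adolescent replacement for the DASS, and the schedule in section 3.7 shows the two on one line separated by a slash.

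**The concern.** The rule is a stated analysis choice, not a detail left open. An SAP that follows section 3.3.3 as written would put the affected measures on a binary scale, and the change-over-time analysis in section 10.3.4 would follow.

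That sits badly with the purpose. To size an RCT on a continuous psychopathology score, the designers need its SD and, for a baseline-adjusted analysis, its baseline-to-follow-up correlation. A binary variable has variance p(1 − p), set by the share positive, and so says nothing about the SD of the score. The association between two binary visits is not the correlation of the scores. What is at stake is whether the feasibility report gives these planning quantities for anxiety and depression, and how precisely change on those scales is described in a small sample.

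**Working it through.** **1. The plan's own figure.** The protocol gives no figure for the efficiency of the binary outcomes. Its one precision figure (section 10.1) concerns adherence, taken to be 70%, and reads "a sample size of 55 patients can estimate a 95% confidence interval for this parameter with 12.2% margin of error". At a rate of 50% the protocol puts the half-width at 13.3%. With half-width = 1.96 × √[p(1 − p)/(n − 1)] and n = 55:

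- p = 0.7: 1.96 × √(0.21/54) = 12.2%, giving 57.8% to 82.2%
- p = 0.5: 1.96 × √(0.25/54) = 13.3%

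Both reproduce (dividing by n gives 12.1% and 13.2%). Neither depends on how questionnaire scores are handled.

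**2. Information kept by a cut.** Assumption: the score is normal. With a share p beyond the cut, c = Φ⁻¹(p) and φ the normal density, the large-sample efficiency of the binary variable relative to the mean of the score is φ(c)²/[p(1 − p)].

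| Share beyond cut | Calculation | Kept | Lost | Patients needed for equal precision |
|---|---|---|---|---|
| 50% | 0.3989²/0.25 | 0.637 | 36% | × 1.57 |
| 30% | 0.3477²/0.21 | 0.576 | 42% | × 1.74 |
| 20% | 0.2800²/0.16 | 0.490 | 51% | × 2.04 |
| 10% | 0.1755²/0.09 | 0.342 | 66% | × 2.92 |

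The best case is the median split, 2/π = 0.637. The shares are illustrative because no cut-off is given. The ratio applies within one instrument, to however many patients complete it.

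**3. Within-person change.** Section 10.3.4 concerns change, so paired data were simulated: 55 patients, 20,000 replicates, normal scores and an assumed mean change of 0.4 baseline SD. Efficiency is the squared ratio of the mean test statistics, binary to continuous.

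| Correlation between visits | 50% above cut at baseline | 80% above cut at baseline |
|---|---|---|
| 0.3 | 0.546 | 0.467 |
| 0.5 | 0.465 | 0.387 |
| 0.7 | 0.352 | 0.289 |

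Under these assumptions the loss for change is about 45% to 71%, more than the median-split figure in step 2.

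**4. What a continuous summary per instrument would give.** The 95% interval for an SD runs from √(df/χ²₀.₉₇₅) to √(df/χ²₀.₀₂₅) times the estimate, with df = n − 1. The age split is not stated, so n per instrument is an assumption:

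- n = 15: 0.73 to 1.58
- n = 28 (an even split): 0.79 to 1.36
- n = 40: 0.82 to 1.28

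These are wide, but usable for planning. The binary variable gives no estimate of the SD at all.

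**5. If the binary form were carried into an RCT.** Assumptions: standardised difference 0.4, 90% power, two-sided 5%.

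- Continuous: 2 × (1.960 + 1.282)²/0.4² = 131.3, so 132 per arm.
- Same shift, score cut where 50% of controls are positive (50% against 34.5%): 211 per arm.
- Cut where 20% of controls are positive (20% against 10.7%): 316 per arm.

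The binary figures use the usual two-proportion formula with pooled variance under the null.

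**6. Which measures fall under the rule.** The protocol names DASS/RCADS only. ESS/ESS-CHAD is declared comparable. The EDE-Q, SREBQ, C-SSRS and EQ-5D-Y are scheduled without separate age versions, and BMI is not a questionnaire score. Y-BOCS/CY-BOCS also has two versions, and the protocol does not say which side of the rule it falls on.

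**The case against.** The strongest reply is that nothing is lost. Raw scores are collected at the scheduled visits, and section 3.5 lists the DASS and the RCADS separately. Sections 3.2, 3.4, 3.5 and 10.3.3 promise summary statistics without limiting them to binary form, so the sentence in 3.3.3 may be meant only for combining age groups. This largely stands. A reader might infer that the plan throws away the SDs a future RCT needs; the documents do not show that. They leave open whether those SDs will be reported.

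A reader might also infer that change in all psychopathology measures will be obscured. Step 6 shows otherwise: an RCT could still be planned on the continuous EDE-Q.

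It is also tempting to say that 55 patients shrink to about 35 (55 × 0.637 = 35.0). That compares with a continuous analysis of all 55 on one scale, which these instruments lack by the protocol's own account. The ratio belongs within each instrument.

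The 36% minimum loss assumes normality; with heavy-tailed scores a median split can lose less. The absence of a cut-off in the protocol is no fault either, since thresholds may stand in the SAP.

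Finally, these outcomes are secondary or exploratory, and the study does not set out to establish efficacy. That limits the consequence. It does not make the binary form a good choice where the continuous one costs almost nothing.

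**Conclusion.** The point holds in a limited form. Section 3.3.3 fixes dichotomisation as the remedy for non-comparable instruments, with DASS/RCADS the only pair named. It does not commit to reporting or modelling the continuous scores that the stated purpose calls for. For roughly normal scores the binary form keeps at most about 64% of the information in a single-visit mean. In the simulated cases it keeps about 29% to 55% for within-person change (change of 0.4 SD, correlations 0.3 to 0.7). It cannot supply the SD or the baseline-to-follow-up correlation.

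The data themselves are safe, and the primary feasibility outcomes, the sample size and every measure outside the rule are untouched. It is an avoidable weakness in secondary and exploratory reporting that should be corrected before analysis.

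The wording on the RCADS adds to it. If adolescents complete both questionnaires, all participants share a continuous DASS score and the reason to dichotomise that pair disappears.

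**What to change.** Replace the sentence in section 3.3.3 with: 'Where adult and adolescent instruments are not comparable, continuous scores will be summarised (mean, SD, change, baseline-to-follow-up correlation) separately by instrument; any binary caseness variable used to combine age groups is supplementary.'

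Note in section 10.4 that this is description by instrument and not a subgroup analysis.

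Reconcile section 3.3.4 with the trial summary and the schedule in section 3.7, stating whether adolescents complete the RCADS alone or the DASS as well.

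The cost is three short text edits and a few more table rows. Samples per instrument are smaller, with the SD precision shown in step 4 of the working; the use of two instruments already implies this. The summaries themselves need no new data collection.
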